10.6.3. Safety

ECG		
ECG Categories		
QTcB and QTcF values at each time point will be reported in categories as below		
ECG Parameter	Units	Category
Absolute		
Absolute QTcF Interval	msec	No Change or Decrease to <=450
		Increase To >450 to <=480
		Increase To >480 to <=500
		Increase To >500
Change from Baseline		
Change from Baseline QTcF	msec	Increase of <=30 ms
		Increase of 31-60 msec
		Increase of >60 msec

10.7. Appendix 7: Reporting Standards for Missing Data

10.7.1. Premature Withdrawals

Element	Reporting Detail
General	
 Participant study completion was defined in the protocol as completion of all phases of the study including the final follow-up visit for the Part for which the participant was enrolled. For the purposes of reporting, a participant is considered to have completed the study if they have not withdrawn and have completed their last scheduled treatment period. If participants prematurely discontinue the study, additional replacement participants may be recruited and assigned to the same treatment sequence at the discretion of the Sponsor in consultation with the investigator. AE and concomitant medication data from participants who were withdrawn from the study will be listed and included in summary tables. Laboratory, vital sign and ECG data from an Early Discontinuation visit will not be included in any summaries but will be listed.

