### 10.1. Sample Size Determination

The sample size is primarily based on feasibility. Approximately 60 participants will be enrolled in the study to obtain approximately 8 randomized participants (6 completers) in each group in Part A and approximately 12 randomized subjects (10 completers) in each group in Part B.

[figure not shown]
The within-subject variability for AUC(0-inf), AUC(0-t) and Cmax of danirixin [GSK Study 201037, GlaxoSmithKline Document Number [2015N248339\\_00](#)] was estimated to be 37.3%, 39.3% and 44.7%, respectively. Based upon the largest within-subject coefficient of variation (44.7% for Cmax of danirixin) and a sample size of 6 subjects completing each group in part A of the study, it is estimated that the half-width of the 90% confidence interval for the ratio of geometric means for the comparison of interest should be no more than 42% of the point estimates. Assuming an observed ratio of one, the corresponding 90% confidence interval for the ratio of geometric means would be 0.70 to 1.42.

A PK interim analysis is planned at the completion of Part A to select the formulation for evaluation in Part B.

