5.2. Baseline Definitions

Any assessments made after the time of the study treatment dose will not be included in the derivation of baseline. Assessments made on the same day as dosing with a missing time are assumed to be taken prior to first dose.

If baseline data are missing, no derivation will be performed and baseline will be set to missing.

Parameter	Baseline Used in Data Display
ECG values	The average of the triplicate readings made on Day -1 of each treatment period will be calculated and used as period baseline. Any reading made after the time of dosing will not be included in the calculation.
Vital signs (pulse rate, systolic and diastolic blood pressure)	The average of the triplicate readings made pre-dose on Day 1 of each treatment period as recorded on the electronic case report form (eCRF) will be used as period baseline
Laboratory data	The assessment made on Day -1 of the first treatment period will be used as a study baseline

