8.2. Clinical Laboratory Analyses

Laboratory displays including chemistry laboratory tests, hematology laboratory tests, urinalysis, and liver function tests will be based on GSK Core Data Standards.

Summaries will include Screening and baseline (see [Section 5.2](#) Baseline Definitions) values, and raw and change from baseline values at the Follow-up visit, and will be split by Part and Group.

Laboratory data from eligibility screening (follicle stimulating hormone, oestradiol, human immunodeficiency virus, hepatitis B & hepatitis C) will not be reported.

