4. Triplicate ECGs at screening and on Day -1 of each treatment period only. Single ECGs at other timepoints (performed at a similar time of day as Day 1 Pre-dose), unless a reading meets the QTc stopping criteria, in which case two further measurements will be taken at the same time point and the average values captured.
5. Triplicate BP and HR at screening and pre-dose on Day 1 of each treatment period only. Single measurements at other timepoints (performed at a similar time of day as Day 1 Pre-dose). HR and BP assessments only performed at the 24 and 48 hr post dose and early discontinuation/follow-up visit timepoints.
6. Meal (where applicable) to be started and completed 30 minutes prior to of danirixin dosing. Meal to consist of 900-1000 calories and be composed of proper caloric content of protein/fat/carbohydrates per FDA guidance and participants will be required to consume at least 90% of meal.
7. When danirixin dosing occurs in the fasted state, participants will be provided with a light snack and then will fast from all food and drink (except water) from 10 hours prior to dosing until 4hrs post-dose on Day 1 in each treatment period at which time lunch will be provided. An evening meal will be provided at approximately 9 h post dose. At all other times during residency in the clinic, meals will be provided at appropriate times.

Part B – Group 2**Periods 1-3**

Procedure		Screening (Up to 30 days prior to Day 1) ¹	Qualification Visit Day -4 ⁹	Day -1	Study Day (Treatment Periods -1-3) ²												Early Discontinuation /Follow-up (3 to 10 days post-last dose)	
					Pre-dose	0h	0.5h	1h	1.5h	2h	3h	4h	6h	8h	10h	12h	24h	
Informed Consent	X																	
Inclusion and Exclusion	X		X															
Demographics	X																	
Full Physical Exam including Height and Weight	X																	
Brief Physical Exam			X															X
Medical History (includes	X		X															

Procedure	Screening (Up to 30 days prior to Day 1) ¹	Qualification Visit Day -4 ⁹	Day -1	Study Day (Treatment Periods -1-3) ²												Early Discontinuation /Follow-up (3 to 10 days post-last dose)	
				Pre-dose	0h	0.5h	1h	1.5h	2h	3h	4h	6h	8h	10h	12h	24h	
substance usage)																	
Pregnancy Test, ³ (WOCBP)	X	X	X														
FSH and estradiol (if needed)	X																
HIV, Hep B and Hep C Screen	X																
Urine Drug Screen	X	X	X														
Alcohol Screen-Breathalyzer	X	X	X														
Urine Cotinine Screen	X	X	X														

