10.10.7. Safety Tables

Safety: Tables					
No.	Population	IDSL / Example Shell	Title	Programming Notes	Deliverable [Priority]
Adverse Events (AEs)					
3.1.	mlTT	CP_AE1x	Summary of On-treatment Adverse Events by System Organ Class and Preferred Term	ICH E3	SAC
3.2.	mlTT	CP_AE1x	Summary All Drug-Related Adverse Events by System Organ Class and Preferred Term	ICH E3	SAC
3.3.	mlTT	AE15	Summary of Common (>=5%) Non-serious Adverse Events by System Organ Class and Preferred Term (Number of Subject and Occurrences)	FDAAA, EudraCT Use TD_AE4VCTR macro	SAC
Serious and Other Significant Adverse Events					
3.4.	mlTT	AE16	Summary of Serious Adverse Events by System Organ Class and Preferred Term (Number of Subjects and Occurrences)	FDAAA, EudraCT Use TD_AE4VCTR macro	SAC
3.5.	mlTT	CP_AE1x	Summary of On-treatment Serious Adverse Events by System Organ Class and Preferred Term		SAC

Safety: Tables					
No.	Population	IDSL / Example Shell	Title	Programming Notes	Deliverable [Priority]
3.6.	mlTT	CP_AE1x	Summary of Adverse Events Leading to Permanent Discontinuation of Study Treatment or Withdrawal from Study by System Organ Class and Preferred Term	IDSL	SAC
Laboratory: Chemistry					
3.7.	mlTT	LB1	Summary of Pre-dose Clinical Chemistry Laboratory Values	ICH E3	SAC
Laboratory: Hematology					
3.8.	mlTT	LB1	Summary of Pre-dose Haematology Laboratory Values	ICH E3	SAC
Laboratory: Urinalysis					
3.9.	mlTT	200163 Table 2.17	Summary of Urinalysis Dipstick Data	ICH E3	SAC
Laboratory: Hepatobiliary (Liver)					
3.10.	mlTT	MH2	Listing of Medical Conditions for Subjects with Liver Stopping Events	Only create if there is a liver event	SAC
3.11.	mlTT	SU2	Listing of Substance Use for Subjects with Liver Stopping Events	Only create if there is a liver event	SAC
3.12.	mlTT	LIVER5	Listing of Liver Monitoring/Stopping Event Reporting	Only create if there is a liver event	SAC
3.13.	mlTT	LIVER6	Listing of Liver Stopping Event Information for RUCAM Score	Only create if there is a liver event	SAC
3.14.	mlTT	LIVER7	Listing of Liver Biopsy Details	Only create if there is a liver event	SAC
3.15.	mlTT	LIVER8	Listing of Liver Imaging Details	Only create if there is a liver event	SAC
3.16.	mlTT	LIVER13	Listing of Subjects Meeting Hepatobiliary Laboratory Criteria	Only create if there is a liver event	SAC
ECG					
3.17.	mlTT	CP_EG9	Summary of Change from Baseline in 2h Post-dose ECG Values	IDSL Include all parameters collected	SAC

Safety: Tables					

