No.	Population	IDSL / Example Shell	Title	Programming Notes	Deliverable [Priority]
3.18.	mlTT	CP_EG11	Frequency of QTc Values at 2h Post-dose by Pre-specified Categories	IDSL Include QTcF, QTcB	SAC
3.19.	mlTT	CP_EG12	Frequency of Change from Baseline in QTc Values at 2h Post-dose by Pre-specified Categories	IDSL Include QTcF, QTcB	SAC
Vital Signs					
3.20.	mlTT	VS1	Summary of Vital Signs	ICH E3	SAC

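### Early Discontinuation laboratory and vital sign values are barred from the summaries, so the only post-dose laboratory summary omits dosed participants who leave early.

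*SAP*

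**What the plan says.** SAP 10.7.1 (Premature Withdrawals) sets the rule: "Laboratory, vital sign and ECG data from an Early Discontinuation visit will not be included in any summaries but will be listed". It gives no reason. The bullet just before it treats other data from withdrawn participants the opposite way: "AE and concomitant medication data from participants who were withdrawn from the study will be listed and included in summary tables".

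For laboratory data, SAP 8.2 limits the summaries to Screening, baseline, and "raw and change from baseline values at the Follow-up visit, and will be split by Part and Group". SAP 5.2 fixes the baseline: "The assessment made on Day -1 of the first treatment period will be used as a study baseline".

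The schedule of activities (Protocol section 2, repeated in SAP 10.2.1) has a single column for Early Discontinuation and Follow-up, with one window and one set of procedures. Its vital sign footnote reads "HR and BP assessments only performed at the 24 and 48 hr post dose and early discontinuation/follow-up visit timepoints".

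The ECG tables in SAP 10.10.7 are tied to one reading: Table 3.17 is "Summary of Change from Baseline in 2h Post-dose ECG Values" and Table 3.18 is "Frequency of QTc Values at 2h Post-dose by Pre-specified Categories". Table 3.19 uses the same time point.

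SAP 8 defines the safety estimand in participants who were randomized and dosed. SAP 2.2 lists safety and tolerability, with clinical laboratory parameters and vital signs among the endpoints, as a primary objective of Part A.

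On attrition, Protocol 10.1 plans for "approximately 8 randomized participants (6 completers) in each group in Part A" and for 12 randomized with 10 completing in each Part B group. Protocol sections 1, 5.1 and 5.2 give about 13 completers out of 16 for Part A.

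**The concern.** The SAP separates data that the protocol collects as one visit, and summarises only the part that comes from participants who stayed. Vital signs have other post-dose time points in the tables. Laboratory values, as SAP 8.2 describes the summaries, do not.

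Two of the protocol's stopping rules act on laboratory results: liver chemistry (8.1.1) and neutrophil count (8.1.3). A participant withdrawn under either would contribute screening and baseline values to the laboratory summary but no value after dosing. In groups of 8 to 12, one such participant matters to a descriptive table on a Part A primary safety endpoint. The data will already have been collected, so the omission arises only from the reporting rule.

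**Working it through.** The plan gives no figure for this loss, so there is none to reproduce. The check traces each safety domain from collection to display, then does simple arithmetic on the planned numbers.

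**Step 1. What the rule removes, by domain.**

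| Domain | Post-dose collection | Planned summary | Removed by SAP 10.7.1 |
|---|---|---|---|
| Adverse events | Through to follow-up | Tables 3.1 to 3.6 | Nothing |
| ECG | 2 h in each period; final visit | Tables 3.17 to 3.19, 2 h only | Nothing from these tables; no final-visit ECG has its own table |
| Vital signs | 24 h and 48 h in each period; final visit | Table 3.20 | Follow-up row only |
| Laboratory | Day -1 of periods after the first; final visit | Tables 3.7 to 3.9, under SAP 8.2 | The only post-dose value summarised |

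Table 3.20 does not name its time points; I assume it has a Follow-up row, as scheduled.

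**Step 2. Laboratory data in detail.** Samples are scheduled at screening, on Day -1 of each period and at the final visit. Day -1 of period 1 is the baseline. Day -1 of later periods follows earlier doses, but SAP 8.2 gives it no place in the summaries. That leaves Follow-up. A dosed participant whose final visit is recorded as Early Discontinuation has no post-dose laboratory value in any summary.

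Tables 3.7 and 3.8 are titled as pre-dose values, which does not fit SAP 8.2. If later Day -1 samples are meant to appear there, the SAP does not say so.

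**Step 3. Whether the listings make up for it.** Listings 22 to 25 (chemistry, haematology) and 31 to 32 (vital signs) cover only participants with a value of potential clinical importance. A withdrawn participant with no such value could have Early Discontinuation results in none of these displays, despite the promise in 10.7.1. Urinalysis (Listing 26) is not restricted in this way.

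**Step 4. Size, from planned numbers.**
- Part A, per group: (8 − 6)/8 = 25%.
- Part A, overall, with 13 completers: (16 − 13)/16 = 18.75%.
- Part B, per group: (12 − 10)/12 = 16.7%.
- Whole study: (2 + 2 + 2 + 2)/40 = 20%, or (3 + 4)/40 = 17.5% with 13 completers in Part A.

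Replacement (Protocol 5.2) lowers the share but not the number missing. If both non-completers in a group were replaced, the shares would be 2/10 = 20% in Part A and 2/14 = 14.3% in Part B.

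**Step 5. After the change.** If every non-completer attended an Early Discontinuation visit, the post-dose laboratory summary would rise from about 6 to 8 per Part A group and from about 10 to 12 per Part B group. The 2 h ECG tables and the 24 h and 48 h vital sign rows would not change.

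**The case against.** The strongest defence is that little is lost. A reader might infer from 10.7.1 that all post-treatment safety tables describe only those who stayed in. The documents do not support that: adverse event tables keep withdrawn participants, Table 3.6 summarises events leading to discontinuation or withdrawal, the ECG tables keep every 2 h reading taken, and the safety tables use the modified intent-to-treat population. This limits the point to the laboratory summary and one vital sign row.

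A reader might also infer that the rule removes precisely the safety withdrawals, QTc cases included. Protocol 8.2 allows withdrawal at the participant's request or for behavioural, compliance or administrative reasons, and nothing says safety reasons will dominate. QTc cases keep their 2 h readings. Liver events have their own displays (Tables 3.10 to 3.16), and the ALT stopping threshold (3 times the upper limit of normal) exceeds the level of potential clinical importance (2 times), so those participants' chemistry is listed. For neutrophils the match is less certain: the stopping rule uses an absolute count and SAP 10.8.1 a percentage.

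Next, no hypothesis is tested, and the laboratory summary is descriptive and split by Part and Group, not by treatment. A bias towards no effect might be inferred but is not shown. Participants at Early Discontinuation will usually have had fewer doses, which is a fair reason to keep the two visit types distinguishable. It is not a reason to leave one out.

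Finally, SAP 8 promises that all collected data enter reporting, and a listing is reporting. That would answer much of the concern if the listings were complete, but for chemistry, haematology and vital signs they are not.

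**Conclusion.** The point holds for the post-dose laboratory summary and the Follow-up vital sign row, and for nothing wider. In those two places the SAP drops collected data from dosed participants without a stated reason, against its own estimand population and on a Part A primary safety endpoint. The direction of any bias depends on why participants leave, which the plan cannot say in advance.

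The percentages above are ceilings on the planned figures, not expected losses. They assume that every planned non-completer attends an Early Discontinuation visit. Some may attend none, and some may miss a critical PK assessment yet still reach Follow-up. The SAP also counts as complete anyone not withdrawn who was dosed in the last scheduled period. The conclusion for laboratory data further rests on reading SAP 8.2 as the full list of summarised time points. It is a modest defect, worth correcting because the remedy is so cheap.

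**What to change.** - In SAP 10.7.1 and 8.2, map Early Discontinuation and Follow-up to one end-of-study visit in the laboratory and vital sign summaries. Flag the visit type, so that participants who had fewer doses can be identified.
- List all Early Discontinuation chemistry, haematology and vital sign data, whether or not the participant has a value of potential clinical importance.
- Reconcile the titles of Tables 3.7 and 3.8 with the Follow-up values that SAP 8.2 promises, and state whether Day -1 values from later periods are shown.

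The cost is a changed sentence or two in the SAP, a visit mapping, a listing note and two table titles. No new data are needed. The one drawback is that the pooled row mixes participants with different numbers of doses, which the flag makes visible.

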10.7.2. Handling of Missing Data

Element	Reporting Detail
General	
 Missing data occurs when any requested data is not provided, leading to blank fields on the collection instrument: 
 These data will be indicated by the use of a “blank” in participant listing displays. If all data for a specific visit is missing the data is excluded from the table/participant listing. Answers such as “Not applicable” and “Not evaluable” are not considered to be missing data and should be displayed as such.
Outliers	
 If outliers are identified, analyses may be repeated excluding the outlying data. Any participants excluded from the summaries and/or statistical analyses will be documented along with the reason for exclusion in the clinical study report.

10.7.2.1. Handling of Missing and Partial Dates

Element	Reporting Detail
General	
 Partial dates will be displayed as captured in participant listing displays.
Adverse Events	
 The eCRF allows for the possibility of partial dates (i.e., only month and year) to be recorded for AE start and end dates; that is, the day of the month may be missing. In such a case, the following conventions will be applied for calculating the time to onset and the duration of the event: 
 Missing Start Day: First of the month will be used unless this is before the start date of study treatment; in this case the study treatment start date will be used and hence the event is considered On-treatment as per Appendix 4: Study Phases. Missing Stop Day: Last day of the month will be used, unless this is after the stop date of study treatment; in this case the study treatment stop date will be used. Completely missing start or end dates will remain missing, with no imputation applied. Consequently, time to onset and duration of such events will be missing.
Concomitant Medications	
 Partial dates for any concomitant medications recorded in the CRF will be imputed using the following convention: 
 If the partial date is a start date, a '01' will be used for the day and 'Jan' will be used for the month If the partial date is a stop date, a '28/29/30/31' will be used for the day (dependent on the month and year) and 'Dec' will be used for the month. The recorded partial date will be displayed in listings.

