8. SAFETY ANALYSES

Details of the planned displays including the population to be used for each display are presented in [Appendix 10](#) List of Data Displays.

The estimand is the effect of actual treatment in the population of participants who were randomized and dosed. All collected data will be included in reporting as described below. If a participant received the incorrect meal or formulation, data will be reported according to the actual meal and formulation received. If a participant consumed <90% of the meal, data will still be reported according to that meal. If a participant was non-compliant with OMP dosing, data will still be reported according to the OMP-containing treatment. Non-recorded missing data following study withdrawal will not be imputed.

All safety data displays will be split by actual treatment received, except where specified below.

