10.4.2. Study Phases for Adverse Event Data

Classification of an AE/SAE as having onset on-treatment will be made with reference to the study treatment dates and the event onset date. If the event onset date is missing, then the event will be considered on-treatment. Events with onset up to 1 day after the date of a treatment will be considered on-treatment.

Study Phase	Definition
Pre-treatment	Events with onset before the first treatment defined as: (onset date < first study treatment dose date or no study treatment dose date)
On-treatment	Events with onset on the day of each treatment and up to 1 day afterwards, defined as: (study treatment dose date <= onset date <= study treatment dose date + 1 or onset date missing)

Events that are not pre- or on-treatment will be presented in listings only

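### The SAP's partial-date rules for AEs assume one treatment start and one stop, so in this 3- or 4-period crossover a stop can precede onset and an event can fall under the wrong treatment or none

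*SAP*

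**What the plan says.** SAP 10.7.2.1 (Handling of Missing and Partial Dates) states: "The eCRF allows for the possibility of partial dates (i.e., only month and year) to be recorded for AE start and end dates". It then gives two rules.

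- **Missing start day:** "First of the month will be used unless this is before the start date of study treatment"; otherwise "in this case the study treatment start date will be used and hence the event is considered On-treatment as per Appendix 4: Study Phases".
- **Stop day missing:** the last day of the month, "unless this is after the stop date of study treatment; in this case the study treatment stop date will be used". Nothing compares the result with the onset date.

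Wholly missing dates are not imputed.

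SAP 10.4.2 defines on-treatment as each dose date and the day after it. It adds: "Events that are not pre- or on-treatment will be presented in listings only". For an absent onset date it says: "If the event onset date is missing, then the event will be considered on-treatment", without naming a treatment. SAP 8 says: "All safety data displays will be split by actual treatment received, except where specified below".

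The design has four single-dose periods in Part A and Part B Group 1, and three in Part B Group 2, with doses at least 5 days apart (Protocol 5.1; SAP 2.3). AEs are collected until the follow-up visit (Protocol 9.2.1), which is 3 to 10 days after the last dose.

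**The concern.** The rules suit a trial with one unbroken spell of treatment. Here treatment is a few isolated dosing days, and neither document says what the start date and stop date of study treatment mean in that setting.

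Two things follow. The stop date can be cut back to a day before the event began. And the start rule ignores the period the event came from, although the period determines which formulation, meal or omeprazole condition the event is counted under. Safety by treatment is an objective in both parts. With about 8 participants per group in Part A and 12 in Part B, one misplaced event changes a cell in the on-treatment AE table (Table 3.1) or the on-treatment SAE table (Table 3.5).

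There is also an anomaly. An event dated only to a month can drop out of the on-treatment tables, while an event with no onset date stays in.

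**Working it through.** The documents give no figure to reproduce, so the check applies the rules as written. Treatment start is taken as the first danirixin dose and treatment stop as the last.

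**Rules as formulas**

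- Imputed start = later of (1st of recorded month, first dose).
- Imputed stop = earlier of (last day of recorded month, last dose).
- An event belongs to period *i* if its onset is dose *i* or the day after. Later events outside every window go to listings only.

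**Worked example:** doses on 20 March, 25 March, 30 March and 4 April (5-day spacing).

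1. Onset 5 April (on-treatment, Period 4), stop recorded as April. Month end, 30 April, is after the last dose, so stop = 4 April, one day before onset.
2. True onset 30 March (Period 3), recorded as March. 1 March precedes the first dose, so start = 20 March and the event is counted under Period 1.
3. True onset 4 April (Period 4), recorded as April. Start = 1 April, outside the windows 30–31 March and 4–5 April, so the event goes to listings only.

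The cap can also contradict a recorded month. With a last dose on 25 June and a stop recorded as July, the imputed stop is 25 June.

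**How often a missing start day goes to the wrong place.** Each first-dose date in a 365-day year was tried, with equal weight on the two on-treatment days of each period.

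- Period 1 events always come out right: the imputed date is the first dose, or the next day if that is the 1st.
- A later-period event comes out right only if the 1st of the month lies in its own window. A dose on the 1st gives two correct onset days. A dose on the last day of a month gives one (the next-day onset). Over 12 months this is 3 × 12 = 36 of 2 × 365 = 730, or 4.9%.
- Overall share correct for *k* periods = [1 + (k − 1) × 36/730] / k. For k = 4: (1 + 3 × 0.0493)/4 = 28.7%. For k = 3: (1 + 2 × 0.0493)/3 = 36.6%.

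The full enumeration agrees and splits the remainder:

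| Periods | Spacing | Correct treatment | Wrong treatment | None (listings only) |
|---|---|---|---|---|
| 4 | 5 days | 28.7% | 56.5% | 14.8% |
| 4 | 7 days | 28.7% | 46.6% | 24.7% |
| 3 | 5 days | 36.6% | 53.5% | 9.9% |
| 3 | 7 days | 36.6% | 46.9% | 16.4% |

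The reverse error also occurs. Events with a true onset in washout or follow-up and a missing start day are imputed as on-treatment in 59% to 85% of cases across the settings tried (follow-up of 3 or 10 days).

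**Missing stop day.** With onset known to be the day after the last dose, the imputed stop precedes onset in every case, although SAP 10.4.2 calls that day on-treatment. The same holds for any later known onset.

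**The case against.** **The conventions are only for time to onset and duration.** The introductory line of 10.7.2.1 says this, but the start-day bullet itself carries the imputed date into the Appendix 4 phases. If imputation did not drive attribution, the SAP would have no rule placing a partially dated event under a treatment.

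**No planned AE table uses duration.** This stands for the stop-date defect. Tables 3.1 to 3.6 are by system organ class and preferred term, and listings show partial dates as captured. At most a derived duration is wrong. A reader might infer that the AE summary tables are corrupted by negative durations; the display list does not support that. The SAP also gives no duration formula, and counting both end days a next-day onset would give zero.

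**Other readings of the treatment dates.** If start and stop are read per period, a next-day onset with a missing stop day fails in every period, and the start rule cannot be used because the period is what is unknown. Protocol 7 and 7.1 allow omeprazole to count as study treatment in Part B Group 2. That moves the stop to about 48 hours after the last danirixin dose and rescues the next-day case there, but not later follow-up onsets.

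**Few events are exposed.** This also stands. Participants are resident from Day -1 to about 24 hours after dosing and return at 48 hours, so on-treatment events are the least likely to lack a day.

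**Conclusion.** The point holds at low severity. Followed literally, the rules can place a stop before a known onset, and they can count a later-period event under the Period 1 treatment or under none. About 29% (four periods) or 37% (three periods) of truly on-treatment events with a missing start day reach the correct treatment. Those figures are conditional on a missing start day, exact 5- or 7-day spacing and equally weighted onset days. They are not expected error rates for this trial, where about 40 participants (16 + 24) are closely observed.

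Two stronger readings are tempting and not supported:

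- **Every event after the last dose gets a stop before its onset.** The failure needs a known onset after the treatment stop date and a missing stop day. Complete stop dates are untouched and wholly missing ones are not imputed. If both days are missing in the last dosing month, the imputed start is no later than the last dose, so the order is preserved.
- **Three in four partially dated events go to the wrong treatment.** That describes four doses in one calendar month with events equally likely in each period. In a 30-day month it covers 15 of 30 first-dose days at 5-day spacing (day + 15 ≤ 30) and 9 of 30 at 7-day spacing (day + 21 ≤ 30). It cannot apply to Part B Group 2, which has three periods.

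The PK analyses are not affected.

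**What to change.** Replace the two rules in SAP 10.7.2.1.

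- **Missing stop day:** use the last day of the recorded month, with no cap at the treatment stop date, and never a date before onset. A cap at the follow-up visit would not do, because SAEs are followed to resolution and a later recorded month would be overridden.
- **Missing start day:** use the stop date and the visit at which the event was first reported to limit the possible dates within the recorded month. Assign the event to the most recent dose on or before the latest possible onset date. If more than one treatment remains possible, apply one prespecified conservative rule, for example counting it as on-treatment under the latest possible treatment, and flag it in the listing. Simply using the period of recording would misplace a washout event first reported at the next admission.

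In the worked example, event 1 then stops on 30 April. If events 2 and 3 are first reported at the 48-hour visits (1 and 6 April), they go to Periods 3 and 4.

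The SAP should name the data field that holds the visit of first report, since the documents do not show one. It should also extend the rule to undated events, which now count as on-treatment with no treatment named.

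The cost is a few SAP sentences and a little programming, with no protocol change. The downside is that some washout events may be counted as on-treatment.
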